19.4.4. ECG ANALYSIS METHODS

The ECG quantitative data will be summarized by incidence of treatment-emergent Grade 3 or Grade 4 QTcF values by treatment arm. Grade 3 and Grade 4 values will be identified prior to averaging the triplicate ECG results.

Subjects who met the abnormal criterion specified in Section 19.4.3 will be identified on the ECG data listing.

19.5. VITAL SIGNS

Vital signs will be recorded once at each visit for subjects who are receiving axitinib. They will be recorded at predose and at 30 minutes post-dose for subjects who are receiving AGS-16C3F. The following vital signs will be collected.

- Sitting Systolic Blood Pressure (mmHg)
- Sitting Diastolic Blood Pressure (mmHg)
- Sitting Pulse Rate (bpm)
- Respiratory Rate (breaths/min)
- Temperature (°C)

Predose body weight (kg) will also be recorded once at each clinic visit for all subjects.

19.5.1. VITAL SIGN SPECIFIC DERIVATIONS

If required, subject body temperature will be converted from Fahrenheit to Centigrade using the formula,

- $^{\circ}\text{C} = 5/9 \times (^{\circ}\text{F} - 32)$

If required, subject body weight will be converted from pounds (lbs) to kilograms (kg) using the formula,

- $\text{kg} = \text{lbs}/2.2$

19.5.2. CTCAE GRADING OF CHANGES IN BODY WEIGHT

Percent changes in subject body weight will be evaluated against the CTCAE criteria presented in Table L.

Table L. Criteria for Evaluation of Changes in Subject Body Weight

CTCAE Term	CTCAE Grade	One or more of the following conditions:
Weight Gain	1	+5% to < +10% change from baseline
	2	+10% to < +20% change from baseline
	3	≥ +20% change from baseline
Weight Loss	1	-5% to > -10% change from baseline
	2	-10% to > -20% change from baseline
	3	≤ -20% change from baseline

19.5.3. VITAL SIGN ANALYSIS METHODS

The maximum weight increase from baseline and maximum weight decrease from baseline (per subject), expressed as an absolute change and a percent change, will be summarized using descriptive statistics. The number and percentage of subjects who met CTCAE criteria for weight gain (Grade 1, 2, or 3) compared to baseline, or weight loss (Grade 1, 2, or 3) compared to baseline, will be presented.

Vital signs will be listed; values which met the CTCAE criteria for Grade 1, 2, or 3 weight gain or weight loss will be identified on the listing.

Clinically important treatment-emergent vital sign values or changes from baseline may lead to the identification and recording of an adverse event.

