### 1.3.2 Comparator Drug - Axitinib (Inlyta®)

Axitinib is an oral kinase inhibitor which has the chemical name *N*-methyl-2-[3-((*E*)-2-pyridin-2-yl-vinyl)-1*H*-indazol-6-ylsulfanyl]-benzamide. Axitinib has been shown to inhibit receptor tyrosine kinases including vascular endothelial growth factor receptors (VEGFR)-1, VEGFR-2, and VEGFR-3 at therapeutic plasma concentrations. These receptors are implicated in pathologic angiogenesis, tumor growth, and cancer progression. VEGF-mediated endothelial cell proliferation and survival were inhibited by axitinib *in vitro* and in mouse models. Axitinib was shown to inhibit tumor growth and phosphorylation of VEGFR-2 in tumor xenograft mouse models [Axitinib U.S. Package Insert (Pfizer Labs), Aug 2014].

Most frequent adverse reactions from a pooled dataset of 672 patients who received axitinib in clinical studies for the treatment of RCC were as follows: diarrhea (55%), hypertension (51%), fatigue (45%), decreased appetite (39%), nausea, weight decrease and dysphonia (33% each), hand-foot syndrome (32%), hemorrhage (26%), hypothyroidism (25%), vomiting (24%), proteinuria (21%), constipation and cough (20% each).

Detailed information on the toxicity associated with axitinib can be found within the Package Insert, Summary of Product Characteristics (SPC) or local product information. Please note the prescribing warnings and precautions for use in patients with cardiac failure, hypertension, thyroid dysfunction, arterial and venous embolic/thrombotic events, elevation of hemoglobin/hematocrit, hemorrhage, gastrointestinal perforation, wound healing complications, posterior reversible encephalopathy syndrome, proteinuria, and liver-related adverse reactions/hepatic impairment.

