### **7.5.3 Vital Signs**

Descriptive statistics will be used to summarize vital sign results for each scheduled time point and changes from baseline by treatment group. Vital signs data will be displayed in listings.

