19.3.4. CTCAE GRADING FOR LABORATORY DATA

Laboratory values for 18 analytes (23 CTCAE terms) will be graded by computer, using the Common Terminology Criteria for Adverse Events (CTCAE) grading system v4.03 (14 June 2010). Table J provides details.

Table J. CTCAE Criteria for Evaluation of Laboratory Values

EDC Collection Analyte	CTCAE Term	
	High	Low
Albumin		Hypoalbuminemia
Alkaline Phosphatase	Alkaline phosphatase increased	
ALT (SGPT)	Alanine aminotransferase increased	
AST (SGOT)	Aspartate aminotransferase increased	
Bilirubin, Total	Blood bilirubin increased	
Calcium	Hypercalcemia	Hypocalcemia
Creatinine	Creatinine increased	
Glucose	Hyperglycemia	Hypoglycemia
Magnesium	Hypermagnesemia	Hypomagnesemia
Phosphorus		Hypophosphatemia
Potassium	Hyperkalemia	Hypokalemia
Sodium	Hyponatremia	Hyponatremia
aPTT	Activated partial thromboplastin time prolonged	
WBC		White blood cell decreased
HGB	Hemoglobin increased	Anemia
PLT		Platelet count decreased
Absolute Neutrophils		Neutrophil count decreased
Absolute Lymphocytes	Lymphocyte count increased	Lymphocyte count decreased

The complete reference document may be found here:

http://evs.nci.nih.gov/ftp1/CTCAE/CTCAE_4.03_2010-06-14_QuickReference_5x7.pdf

It is expected that incomplete data will result in a missing CTCAE Grade.

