19.3.5. LABORATORY ANALYSIS METHODS

Presentations will use SI Units. Quantitative laboratory measurements reported as “<X”, i.e. below the lower limit of quantification (BLQ), or “>X”, i.e. above the upper limit of quantification (ULQ), will be converted to X for the purpose of quantitative summaries, but will be presented as recorded, i.e. as “<X” or “>X” in data listings.

The following summaries by treatment arm will be provided for laboratory data:

- Incidence of Grade 3 and Grade 4 toxicities, based on the CTCAE grading system, at each subject's worst post-baseline value, safety follow-up assessment, and final assessment
- Shift tables from baseline toxicity grade to worst post-baseline toxicity grade, based on the CTCAE grading system

Listings of all laboratory data collected during the study will be produced. Any positive pregnancy tests will be listed separately.

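### The SAP replaces the protocol's by-arm vital-sign summary with a listing and does not log the change, so blood pressure has no planned by-arm table

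*SAP*

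**What the plan says.** Protocol 7.5.3: "Descriptive statistics will be used to summarize vital sign results for each scheduled time point and changes from baseline by treatment group". Vital signs are also part of the secondary safety endpoint (Protocol 2.3.2). SAP 2.3 names them, with adverse events, ECG and laboratory results, as a basis for comparing AGS-16C3F with axitinib.

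SAP 19.5 lists systolic and diastolic pressure, pulse, respiratory rate and temperature, and adds body weight. Protocol 5.6.1 has them taken once per clinic visit on axitinib, and predose and about 30 minutes post-dose on AGS-16C3F dosing days.

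SAP 19.5.3 then summarizes weight: "The maximum weight increase from baseline and maximum weight decrease from baseline (per subject), expressed as an absolute change and a percent change" gets descriptive statistics, and weight gain or loss is counted by CTCAE grade. For everything else the plan is a listing: "Vital signs will be listed; values which met the CTCAE criteria for Grade 1, 2, or 3 weight gain or weight loss" are marked there.

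For laboratory data, SAP 19.3.5 plans two by-arm summaries: "Incidence of Grade 3 and Grade 4 toxicities, based on the CTCAE grading system", and "Shift tables from baseline toxicity grade to worst post-baseline toxicity grade, based on the CTCAE grading system". SAP 19.3.4 states which values can enter them: "Laboratory values for 18 analytes (23 CTCAE terms) will be graded by computer". Protocol 7.5.2 plans the same two kinds of summary.

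**The concern.** Two things look wrong in the vital-sign plan. The SAP withdraws a summary that the protocol commits to, and it does so without an entry in its own log of changes. It also leaves the SAP's safety objective without the by-arm table of measured vital signs that the objective presupposes.

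Blood pressure is where this matters. Protocol 1.3.2 gives hypertension as the second most frequent axitinib reaction in its pooled data and names it among the prescribing warnings. SAP 19 plans no statistical safety comparison between arms unless a section says otherwise, so the by-arm tables are the comparison. Without a blood-pressure table, hypertension enters only when an investigator, who knows the treatment, reports it as an adverse event.

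A related gap, of a different kind, affects thyroid function and urine protein. Both are measured every odd cycle in both arms (Protocol 5.2.6), and hypothyroidism and proteinuria are also listed axitinib reactions, but neither measurement has a planned table in either document.

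**Working it through.** **1. Vital signs, protocol against SAP.**

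| Variable | Protocol 7.5.3 | SAP 19.5.3 |
|---|---|---|
| Systolic pressure | by visit and change, by arm | listing |
| Diastolic pressure | by visit and change, by arm | listing |
| Pulse | by visit and change, by arm | listing |
| Respiratory rate | by visit and change, by arm | listing |
| Temperature | by visit and change, by arm | listing |
| Body weight | weight not named in 7.5.3 | maximum change and CTCAE grade |

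So 0 of 5 vital signs other than weight keep a table.

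**2. Was the change logged?** Table A (SAP 3.3) records items as small as the order of the secondary endpoints and the replacement of the word hiatus. It also records another dropped summary, prior medications (Protocol 7.3.4). It has no entry for Protocol 7.5.3.

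**3. Laboratory tables.** The parameters in SAP 19.3.1 are 10 hematology, 20 chemistry, 1 spot urine, 4 from the 24-hour urine collection, 3 coagulation and 2 thyroid: 10 + 20 + 1 + 4 + 3 + 2 = 40. Table J holds 18 analytes, which reproduces the stated 18. Ungraded: 40 − 18 = 22, including TSH, free T4, uPCR and 24-hour protein. Both summaries in SAP 19.3.5 use CTCAE grades, so these four have no planned table. The low/normal/high classes derived in SAP 19.3.3 feed no summary in 19.3.5. Because Protocol 7.5.2 is limited in the same way, this is a gap shared by both documents, not a departure. (Table J as read has 25 filled cells against the stated 23 terms; that does not affect this point.)

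**4. Scale only.** Assume half of about 134 subjects, 67, receive axitinib and the pooled rates in Protocol 1.3.2 carry over:

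- hypertension: 67 × 0.51 = 34.2
- hypothyroidism: 67 × 0.25 = 16.8
- proteinuria: 67 × 0.21 = 14.1

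These are reported adverse reactions. They show that the toxicities should be common in the control arm. They do not count subjects missing from the tables.

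**5. Which readings would enter a table.** On dosing days AGS-16C3F subjects have two readings per visit and axitinib subjects one. SAP 6.4 defines worst post-baseline over all values after the first dose, so by default it would take the worst of about twice as many readings in the AGS-16C3F arm. A shift table must override that default.

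**The case against.** The other side has good points.

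- **The adverse-event route is not arbitrary.** Under Protocol 5.7.1 an abnormal finding is an adverse event if it causes symptoms, needs active intervention or interrupts drug; only the fourth criterion is investigator opinion. Treated hypertension therefore qualifies. Concomitant medication is summarized by arm to ATC Level 4 (SAP 14), and all values are listed. This stands, and it limits the harm. It does not replace a table of measured pressures.
- **The laboratory plan follows the protocol.** This stands in full: the TSH, free T4 and uPCR tables are an optional improvement.
- **Not everything is visible.** SAP 8 refers to table templates that are not in the documents, and SAP 19.3.5 has a rule for values reported as below or above a limit in quantitative summaries that it never names. The SAP was written to protocol version 4.0, while the protocol at hand is version 6.0. A template might hold the missing table, and 7.5.3 might have read differently. The amendment text available shows no change to 7.5.3. This lowers confidence but leaves the conflict in the text.
- **It is a Phase 2 proof of concept.** No primary conclusion changes.

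A reader might go further and infer that axitinib's main toxicities in general lack measured by-arm tables, so that the comparison is tilted against AGS-16C3F. The documents do not support that. Weight decrease (33% in Protocol 1.3.2) has its own table. Elevated hemoglobin, ALT, AST and bilirubin, which bear on the protocol's axitinib warnings, are computer-graded in both arms.

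**Conclusion.** The conflict between Protocol 7.5.3 and SAP 19.5.3 is real, unlogged and worth correcting. Its size is five vital signs, two of them blood pressures, with no planned by-arm table in a trial where safety against axitinib is a secondary objective. It does not touch the primary endpoint. The conclusion rests on the SAP text as the full plan and on 7.5.3 having read the same in protocol version 4.0.

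A reader might apply an assumed non-reporting fraction to the 34, 17 and 14 expected cases to estimate how many subjects drop out of the comparison. That is not valid. The rates already count reported reactions, so those cases would be in the adverse-event tables. If R cases are reported and a fraction u of all cases is not, the number missed is R × u/(1 − u), and the documents give no value for u. Protocol 1.3.2 also gives no exposure time for its rates. No number of missed cases should be quoted.

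**What to change.** 1. In SAP 19.5.3, restore the Protocol 7.5.3 summary: at minimum systolic and diastolic pressure, value and change from baseline, by scheduled visit and arm. Use the predose reading for AGS-16C3F, so each arm contributes one reading per visit. If the sponsor prefers to leave pulse, respiration or temperature as listings, enter that in Table A with a reason.
2. Add a by-arm shift from baseline to worst post-baseline blood-pressure category, and state that predose readings replace the SAP 6.4 default. Write the category limits into the SAP. The documents do not print CTCAE blood-pressure cut-offs. The protocol's 150/90 is an eligibility rule needing two readings at least an hour apart, so it cannot be applied to a single visit reading without saying so.
3. Optional, in SAP 19.3.5: by-arm shift tables for TSH and free T4 using the low/normal/high classes from SAP 19.3.3, with the direction of worst stated. Add a shift for uPCR (below 2.0 against 2.0 or more) from baseline to worst. It must be a shift, not a post-baseline count, because inclusion criterion 10 admits subjects at 2.0 or more if 24-hour protein is below 2 g; they should not count as new.

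Cost: three or four extra tables, all from data already collected; no new assessment.

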19.6. PHYSICAL EXAMINATIONS

Post-baseline abnormalities will be reported as adverse events. Physical examination results will be listed by treatment group.

19.7. OTHER SAFETY ASSESSMENTS

19.7.1. OPHTHALMOLOGIC EXAMS

A complete eye exam is planned to be performed at Baseline for all subjects, at end of Cycle 2, end of Cycle 6, and at Safety Follow-up for AGS-16C3F subjects, and at other times if clinically indicated for any subject. Results will be collected on the Eye Exam eCRF page. The following types of data will be collected.

- Ophthalmology Symptoms
- Visual Acuity
- Extraocular Movement
- Tonometry
- External Exam
- Slit Lamp Exam
- Dilated Fundus Exam
- Optional Exams
- Impression
- Visual Acuity Grade
- Ocular Diagnoses and Ophthalmology Outcome, including the diagnosis, event status (new, ongoing, resolved), relatedness to study drug, prescribed treatment, and action taken with study treatment due to the eye exam results.

In general, eye-related summaries by timepoint will include data from both planned and PRN assessments. Determinations at each timepoint will include all eye data collected since the previous planned assessment. The screening period will include eye assessments performed within 28 days prior to the first dose of study drug. For subjects who receive AGS-16C3F, Day 43 will include the worst value recorded for each subject from post-dose

C1D1 through Predose C3D1, inclusive. Day 106 will include the worst value recorded from Post-dose C3D1 through C6D1, inclusive. Subsequent intervals will be defined similarly at 3-cycle intervals during treatment. For subjects who receive axitinib, Day 43 will include the worst value recorded for each subject from Day 1 through Day 43 (± 7 days). Day 106 will include the worst value recorded from the Day 43 assessment date + 1 through Day 106 (± 7 days), inclusive. Subsequent intervals will be defined similarly at 63-day intervals during treatment. Data collected after the decision to end treatment for AGS-16C3F subjects or after the date of last dose for axitinib subjects are considered to be “end of treatment and beyond”.

Ocular symptoms recorded during the complete eye exam will be coded using the MedDRA Version 18.1 dictionary. The first post-baseline occurrence of any ocular symptom and of each ocular symptom will be summarized over time. The number of subjects at risk in each time interval, the adjusted conditional probability of experiencing the symptom for the first time in an interval, the cumulative probability of experiencing the specified symptom for the first time from the time of first dose through the end of the interval, and the total number of reports of the symptom in the specified interval will be presented in a table. The number of reports will include multiple reports per subject where applicable.

Detailed visual acuity measurements (e.g., 20/20 or 20/40, etc.) and Investigator’s Impression will be listed but not summarized.

Visual acuity changes from baseline, represented by the number of lines of change from baseline (see Table M), will be summarized by treatment arm and assigned ocular AE grade, by eye and overall for both eyes. The investigator’s determination of changes in visual acuity and the ocular AE grade of any changes will be used in all analyses. The number and percentage of subjects who had a change which qualified as a Grade 1, 2, 3, or 4 change will be summarized at each planned timepoint, for the worst post-baseline value, and at the final assessment. [Note: Subjects are not expected to improve from baseline. Cases of improvement will be returned to Data Management for investigation.]

Abnormalities of extraocular movement, pupil exam, tonometry (IOP), external exam, slit lamp exam (cornea, lens, lids and lacrimation, conjunctive and sclera, anterior chamber, iris, vitreous, other), and dilated fundus exam (disc, disk/cup ratio, macula, vessels, periphery) will be summarized at each planned visit, at the worst value, and at the final assessment, by the number and percentage of subjects having abnormalities in each eye (where applicable) and in both eyes. In the case of intraocular pressure, IOP >21 mmHg in an eye will be considered abnormal (Chang DF 2011). If both the right eye and the left eye meet this criterion, then “both eyes” will be considered abnormal. The categories of “abnormal at baseline”, “abnormal, same as previous”, and “abnormal, new or change from previous” will be derived for the IOP. In the case of the dilated fundus exam, statistics will be generated for exams performed with dilation and without dilation.

Results from optional exams (corneal pachymetry, Schirmer, corneal topography, endothelial evaluation, and other diagnostics) will be listed.

Ocular diagnoses will be coded using the MedDRA Version 18.1 dictionary. The number and percentage of subjects who had any ocular diagnosis during the study and the number and percentage who had each unique diagnosis (based on the PT) will be reported by treatment arm. The statistics will be provided for all diagnoses and also for drug-related diagnoses.

Ocular diagnoses will be reported (along with the investigator’s Visual Acuity Grade and the data from the Ophthalmologic Outcome” section of the eCRF) as ocular adverse events. The reporting of these events is addressed in Adverse Events (Section 19.1). Grading of these events is presented in Section 19.7.1.1.

Complete eye exam data as collected will be presented by subject in a data listing. No data will be imputed.

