6.4. DERIVED TIMEPOINTS

For subjects in the AGS-16C3F group, each infusion date starts a new cycle. Cycles are numbered consecutively. For subjects in the axitinib group, clinic visits and most other events are identified by the planned study day.

The following derived visit definitions will apply to tables, figures, and listings unless otherwise specified for a particular analysis:

- **Worst Post-Baseline:** The worst value collected in the period from C1D1 post-dose through the later of the safety follow-up visit or the last dose date + 28 days (inclusive).
- **Safety Follow-Up:** Everyone is required to have an actual safety follow up visit and one measurement for the safety f/u. For subjects who don't have a safety F/U visit, report the worst value recorded during the period from the day of last dose or decision to end treatment through the subject's last available assessment.
- **Final Visit:** The chronologically last available assessment.
- **Any Time during Treatment/Safety Follow-up:** From C1D1 post-dose through the later of the safety follow-up visit or the last dose date + 28 days (inclusive).

Eye assessments are identified in the raw data only by the exam date. Data from the AGS-16C3F subjects will be assigned to a Cycle based on comparing the exam date to the infusion dates. Data from the axitinib subjects will be assigned to a scheduled assessment or identified as a PRN exam, based on the calculated study day of the exam (see Section 6.6, Visit Windowing Conventions).

For tables that show eye-related safety results by timepoint during the study, data from the AGS-16C3F subjects will be grouped for analysis as follows: Day 43 will include data recorded from post-dose C1D1 through Predose C3D1, inclusive; Day 106 will include data recorded from Post-dose C3D1 through Predose C6D1, inclusive; subsequent intervals will be defined similarly at 3-cycle intervals during treatment. For the axitinib subjects, the analysis periods are based on the scheduled/PRN classifications that have been assigned. For both groups, assessments that are made after the end of treatment (EOT) will be grouped together as "EOT and beyond". Both planned and PRN eye assessment data will be included in all intervals.

It may be necessary to derive other timepoint records for some analyses. Where applicable, these are specified for each analysis that requires them.

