19.1. ADVERSE EVENTS

Treatment emergent adverse events (TEAEs) are defined as AEs that started or worsened in severity after the first dose of study drug and until 28 days post the last administration of the study drug or the subject's Safety Follow-Up visit, whichever occurred later. Events that begin on Day 1 will be counted as treatment-emergent.

AEs will be coded to system organ class (SOC) and preferred term (PT) using the Medical Dictionary for Regulatory Activities (MedDRA) Version 18.1 central coding dictionary and will be graded according to the National Cancer Institute (NCI) Common Toxicity Criteria for Adverse Events (CTCAE), version 4.03.

All summaries of AEs will include only treatment-emergent events unless otherwise stated.

Safety will be evaluated based on the incidence of AEs (including Grade 3 and Grade 4 AEs, treatment-related adverse events, serious adverse events, and AEs requiring discontinuation of study treatment). The number and percentage of AEs, SAEs, AEs leading to discontinuation of study treatment, and AEs related to study drug will be summarized by SOC, PT and treatment group. The number and percentage of AEs by severity will also be summarized. Listings of AEs, SAEs, deaths, and events leading to discontinuation of study treatment will be presented.

See Appendix 2 for handling of partial dates for AEs. In the case where it is not possible to define an AE as treatment emergent or not, the AE will be classified by the worst case; i.e. treatment emergent.

An overall summary of the number and percentage of subjects who had events in each of the categories described below will be produced by treatment group and for combined treatment groups.

- Subjects with at least one AE
- Subjects with at least one possibly drug-related AE
- Subjects with at least one AE of CTCAE Grade 3 or Grade 4
- Subjects with at least one possibly drug-related AE of CTCAE Grade 3 or Grade 4
- Subjects with at least one serious AE
- Subjects with at least one possibly drug-related serious AE
- Subjects whose treatment had to be modified due to an AE
- Subjects whose treatment had to be modified due to a possibly drug-related AE
- Subjects who discontinued treatment with study drug because of an AE
- Subjects who discontinued treatment with study drug because of a possibly drug-related AE
- Subjects with at least one AE resulting in death

- Subjects with at least one possibly drug-related AE resulting in death

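### The eye-exam symptom and ocular diagnosis tables in SAP 19.7.1 do not separate findings present at screening from new ones

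*SAP*

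**What the plan says.** Two descriptive tables in SAP 19.7.1 are at issue.

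- **Symptoms recorded at the complete eye exam.** The event is defined as follows: "The first post-baseline occurrence of any ocular symptom and of each ocular symptom will be summarized over time". The table reports "The number of subjects at risk in each time interval", a conditional probability per interval, and "the cumulative probability of experiencing the specified symptom for the first time from the time of first dose through the end of the interval". Nothing says who is at risk at the start.
- **Ocular diagnoses.** The table gives "The number and percentage of subjects who had any ocular diagnosis during the study", then the same by preferred term, for all diagnoses and for drug-related ones. No post-baseline or treatment-emergent limit is stated.

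The eye-exam form records each diagnosis with its "event status (new, ongoing, resolved"), and SAP 12.4 collects ocular history with start dates and an ongoing flag. No rule for the two tables uses either source. For intraocular pressure, by contrast, 19.7.1 derives separate categories for abnormal at baseline, unchanged, and new or changed.

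Ocular diagnoses are also to be reported as ocular adverse events. On that, 19.7.1 states: "The reporting of these events is addressed in Adverse Events (Section 19.1"). SAP 19.1 defines treatment-emergent events as "AEs that started or worsened in severity after the first dose of study drug" and limits adverse event summaries to them unless otherwise stated.

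**The concern.** Ocular toxicity is what the protocol (1.4) calls the compound's main distinctive toxicity, reported in 12 of 13 Phase 1 subjects at 1.8 mg/kg, and SAP 2.3 makes ocular safety an objective. A reader will take the symptom table as showing how often, and how soon, eye symptoms begin on treatment, and the diagnosis table as showing what eye disease developed.

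Pre-existing findings will be present. Protocol 5.6.5 foresees subjects with dry eyes at screening, and exclusion criterion 5 bars only certain eye conditions; glaucoma, for example, is barred only if uncontrolled. A dry eye noted at screening and noted again at the first post-baseline exam satisfies the symptom table's wording as a first post-baseline occurrence. If such cases are counted, the tables report a mixture of prevalence and onset. Two programmers could also build different risk sets from the same text.

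**Working it through.** The documents give no ocular rate or sample size calculation for these tables, so there is no stated figure to reproduce. The check has two parts.

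**1. Which outputs are open to the problem**

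| Output | Rule that removes baseline findings | Open? |
|---|---|---|
| Symptom table (19.7.1) | None; risk set undefined, clock from first dose | Yes |
| Diagnosis table (19.7.1) | None stated | Yes |
| General AE tables (19.1) | Treatment-emergent only; Appendix 2 drops a known start before first dose | No, when onset is known |
| Visual acuity Grades 2 to 4 (19.7.1.1) | Graded on change from screening | No |
| Grade 1 in the separate eye-exam tables (19.1.6, 19.7.1.1) | Grade 1 is a finding with no acuity change; the treatment-emergent limit is not restated | Possibly |
| Intraocular pressure (19.7.1) | Baseline, same and new categories derived | No |

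One loose end concerns dates. SAP 6.4 says "Eye assessments are identified in the raw data only by the exam date", and Appendix 2 assumes an adverse event to be treatment-emergent when both its start and stop dates are missing.

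**2. Illustration of size**

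Let b be the share of subjects with the finding at screening, r the probability that it is recorded again after baseline, and q the true new-onset risk in those free of it.

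- Literal rate = b·r + (1 − b)·q
- Rate with baseline cases removed from the risk set = q
- Excess = b·r + (1 − b)·q − q = b·(r − q)

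Assumptions: b = 5 to 30% and r = 0.5 to 1. For q I use 10% (assumed) and 54%, the Phase 1 dry eye frequency at 1.8 mg/kg (protocol 1.3.1.2), as a high value only. An arm is 134/2 = 67 subjects.

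| b | r | Literal rate, q = 10% | Excess (points) | Subjects per 67 | Excess (points), q = 54% |
|---|---|---|---|---|---|
| 5% | 0.5 | 12.0% | +2.0 | 1.3 | −0.2 |
| 5% | 1 | 14.5% | +4.5 | 3.0 | +2.3 |
| 10% | 0.5 | 14.0% | +4.0 | 2.7 | −0.4 |
| 10% | 1 | 19.0% | +9.0 | 6.0 | +4.6 |
| 20% | 0.5 | 18.0% | +8.0 | 5.4 | −0.8 |
| 20% | 1 | 28.0% | +18.0 | 12.1 | +9.2 |
| 30% | 0.5 | 22.0% | +12.0 | 8.0 | −1.2 |
| 30% | 1 | 37.0% | +27.0 | 18.1 | +13.8 |

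The excess is positive only when r exceeds q. With common onset and incomplete re-recording it disappears or turns slightly negative.

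**Between arms.** Protocol 5.6.5 schedules post-baseline exams for AGS-16C3F subjects; axitinib subjects have them only when clinically indicated. With equal b and q in both arms, the literal difference is b·(r for AGS-16C3F − r for axitinib). Taking r = 1 against r = 0.1 to 0.5 (assumed), this runs from 0.05 × 0.5 = 2.5 points to 0.30 × 0.9 = 27 points, with no true difference.

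**The case against.** The strongest reply is that the SAP is silent here and does not prescribe a wrong count. The symptom table speaks of subjects at risk and of experiencing a symptom for the first time, and a careful programmer could read that as excluding anyone who already had it. For diagnoses, the text does not say that screening exams count, and recording relatedness to study drug beside each diagnosis suggests on-treatment exams. Ocular history is already summarised by arm, including ongoing conditions (SAP 12.4); drug-related diagnoses are shown separately; a full eye-exam listing is planned; and safety data are not formally compared between arms (SAP 19).

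Much of this stands: it lowers the stakes and shows that the better reading is available. It does not settle the matter. The stated event is the first post-baseline occurrence and the stated clock starts at first dose, so the literal reading includes persisting findings. Separate history tables and listings do not let a reader subtract baseline cases from a cumulative probability.

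A reader might go further and infer that pre-existing disease is counted as ocular adverse events, so that ocular toxicity rates in general are inflated. The documents do not support that: 19.7.1 refers ocular diagnoses reported as adverse events to 19.1, whose treatment-emergent limit then applies, and acuity Grades 2 to 4 are relative to screening.

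A reader might also infer that an equal background is added to both arms and hides the contrast. At b = 30% with every case counted, 54% against 10% would read 0.30 + 0.70 × 0.54 = 67.8% against 0.30 + 0.70 × 0.10 = 37.0%, so the ratio would fall from 5.4 to 1.8. That holds only if screening exams count in the diagnosis table, which is not stated. It also uses, as an onset risk, a Phase 1 adverse event frequency from 13 subjects.

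**Conclusion.** The point holds for two tables: eye-exam symptoms and ocular diagnoses in SAP 19.7.1. Read literally, they mix findings present at screening with new ones. Grade 1 in the separate eye-exam tables may be affected as well. The general adverse event tables with known onset dates are not.

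Size and direction cannot be derived, because the documents give none of b, r or q. Under the assumed ranges, a true onset risk of 10% would be overstated by 2 to 27 points. At 54% the error runs from about −1 to +14 points, so inflation is not certain. The more awkward consequence is between arms: unequal exam schedules could by themselves produce a false difference of 2.5 to 27 points against AGS-16C3F under the stated assumptions. The primary PFS analysis is untouched. The correction is worth making because it is cheap and concerns the toxicity of most interest.

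**What to change.** In SAP 19.7.1:

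- **Symptom table.** For each symptom, define the risk set as subjects without that symptom at the last exam before first dose. For any symptom, count the first one not present at baseline.
- **Diagnosis table.** Count preferred terms first recorded after first dose with status new, and absent both from the screening exam and from ongoing ocular history. Show baseline and ongoing diagnoses in a separate column.
- **Separate eye-exam tables.** State that the treatment-emergent rule of 19.1 applies to them too, with the exam date taken as onset where no other date exists.

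Do not build the rule on a worsened status: the status values listed are new, ongoing and resolved only.

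The cost is SAP wording and some programming; exam dates, event status and ocular history are already collected. The downside is a smaller risk set for common symptoms. The change does not remove the unequal chance of detecting new findings that comes from the different exam schedules, so the tables should carry a note to that effect.
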